2.0 OBJECTIVES AND SCIENTIFIC AIMS

The objective of this study is to validate methods of delivering adequate conformal dose to spinal and pelvic targets with HDR catheters using image-guided navigational techniques.

The Specific Aims of this study are to:

1. Verify feasibility of HDR treatment of spinal and/or pelvic lesions using catheters placed under image-guided navigational techniques, to provide improved dosimetric coverage of lesions such that
 - a. Gross Target Volume (GTV) D90 \geq 80%
 - b. Cord/Cauda max dose (Cord/Cauda Dmax) of < 8 Gy

Secondary objectives:

1. Demonstrate safety of HDR brachytherapy for previously irradiated lesions of the spine and/or pelvis, defined as an acceptable level of severe toxicity (both acute and late effects) in the setting of HDR brachytherapy treatment. Severe toxicity will be defined as \geq grade 3 NCI CTCAE v 4.0 toxicity that is at least possibly related to treatment (see Appendix 2).
2. Assess patient pain scores referable to the treatment site using the standardized 11-point pain scale.
3. Assess patients for duration of in-field progression-free survival at the treatment site.

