11.0 TOXICITIES/SIDE EFFECTS

For non-serious adverse events, we will only be capturing the toxicities that are possibly related to protocol treatment. The National Cancer Institute (NCI) Common Terminology Criteria for Adverse Events (CTCAE) version 4.0 will be used as an instrument to evaluate toxicities, discussed in section 12.

The toxicities associated with radiation therapy to the spine or pelvis can be classified as either early (occurring within 90 days of the treatment) or late toxicities (after 90 days to 1 year). Mild acute toxicities that are expected from treatment include Grade 1-2 fatigue and irritation at the sites of catheter insertion, as well as a generally transient pain flare in the treated bone site. Less likely (<5% of the time) would be infection or bleeding at the sites of catheter insertion. Rare but serious (<1%) acute toxicities could include complications such

MEMORIAL SLOAN-KETTERING CANCER CENTER IRB PROTOCOL #: 12-260 A(4)

as perforation of a visceral organ during catheter placement (lung, bowel, or kidney) or fractures in the bones of the spine.

There are two types of toxicity which will be considered as potentially serious adverse events from the brachytherapy treatment: neurologic and musculoskeletal. These generally occur late and include myelitis or pathologic fractures of the bones of the spine and/or pelvis. Neurologic and musculoskeletal toxicities will be evaluated with the National Cancer Institute (NCI) Common Toxicity Criteria v4.0 (discussed in section 12, also see Appendix 2 for specifics). The probability of severe (\geq grade 3) neurologic and musculoskeletal toxicity is expected to be less than 10%, which is below the currently observed rate of severe toxicity reported by patients who undergo standard radiation therapy for lesions of the spine at MSKCC.

DEFINITIONS

1. Definition of an Adverse Event (AE)
 - a. An Adverse Event is defined by the GCP (Guide to Good Clinical Practice) as any undesirable experience occurring to a subject during a clinical trial, whether or not it is considered related to the investigational product(s). In this trial we will only document those AEs that are at least possibly related to protocol therapy.
2. Definition of a Serious Adverse Event (SAE)
 - a. A Serious Adverse Event is an adverse experience that:
 - i. is fatal or life-threatening
 - ii. is disabling

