 - iii. results in hospitalization or prolongation of hospitalization, with the exception of an overnight admission following the procedure.
 - iv. results in a congenital anomaly or occurrence of malignancy
 - b. Any neurologic and musculoskeletal toxicity that is grade 3 or higher will be considered a serious adverse event.
3. Definition of an Unexpected Adverse Event
 - a. An Unexpected AE is an experience not previously reported (in nature, severity, or incidence) in the current Investigator's Brochure or general investigational plan.

Evaluation of SAE:

Review of the patient record including the treatment dosimetry will be undertaken by the principal investigator with the assistance of the co-principal investigator and at least one investigator from both Medical Physics and Radiology. The principal investigator may decide to continue the protocol without modification, discontinue the study altogether, or to modify the protocol prior to enrolling more patients pending the results of the review.

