NCI Common Toxicity Criteria. The NCI scales are simple to complete and provide a means for assessing patient symptoms. For the purposes of this study, the musculoskeletal panel of questions will be limited to those pertaining to back pain and myositis (see Appendix 2). To evaluate neurological toxicities, the categories will be limited to cerebrospinal fluid leak and myelitis (see Appendix 2). Only the CTCAE v4.0 will be used in toxicity grading.

Numeric Rating Scale (NRS-11). The NRS-11 numeric rating scale is a validated tool for discriminating pain level, in which patients rank their "pain score" on a scale of 0 to 10, where 0 is equivalent to "no pain," and 10 is "unbearable pain." [Downie 1978, Paice 1997]

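### Section 12.0 narrows the toxicity terms to four and leaves out fracture and nerve injury that the protocol itself names, so a safety summary built on those terms could omit them (minor)

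*Combined protocol and SAP*

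**What the plan says.** Section 12.0, in its paragraph on the NCI Common Toxicity Criteria, states that "the musculoskeletal panel of questions will be limited to those pertaining to back pain and myositis". For neurological toxicity it states that "the categories will be limited to cerebrospinal fluid leak and myelitis". Both sentences cite Appendix 2, and the paragraph closes by making CTCAE v4.0 the only grading scale.

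Section 11.0 treats neurologic and musculoskeletal toxicities as the two potentially serious kinds and says of them: "These generally occur late and include myelitis or pathologic fractures of the bones of the spine and/or pelvis". For their grading it refers the reader onward ("discussed in section 12, also see Appendix 2 for specifics"). It says the probability of severe "neurologic and musculoskeletal toxicity is expected to be less than 10" per cent. Its definitions add "Any neurologic and musculoskeletal toxicity that is grade 3 or higher will be considered a serious adverse event" and "In this trial we will only document those AEs that are at least possibly related to protocol therapy".

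Section 2.0 defines severe toxicity, for the first secondary objective, as at least "grade 3 NCI CTCAE v 4.0 toxicity that is at least possibly related to treatment", and then points to Appendix 2. Section 3.4 names the cord, cauda equina, exiting peripheral nerves, paraspinal muscle and vertebral bodies as tissues at increased risk in previously irradiated patients. Section 14 halts the study at a second serious adverse event, defined as grade 3 or higher or as set out in Section 11.0.

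**The concern.** Section 11.0 gives two examples of the toxicities that matter most, myelitis and pathologic fracture. The section to which it delegates grading keeps the first and drops the second. Injury to the cauda equina or a peripheral nerve, named in Section 3.4, has no term of its own either. A team that follows Section 12.0 literally would have no listed term under which to grade these events.

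Safety is the first secondary objective. At stake is whether the reported severe-toxicity rate covers the same events as the expectation in Section 11.0, which is stated for neurologic and musculoskeletal toxicity as a whole.

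**Working it through.** **1. Named toxicities against the Section 12.0 terms.**

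| Toxicity the protocol names | Where | Among the four terms? |
|---|---|---|
| Myelitis | 11.0 | Yes |
| Late pathologic fracture, spine or pelvis | 11.0 | No |
| Acute spine fracture | 11.0 | No |
| Cauda equina or exiting peripheral nerve injury | 3.4 | No |
| Vertebral body injury | 3.4 | Only through back pain as a symptom |
| Paraspinal muscle injury | 3.4 | At least partly, through myositis |

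**2. Which definitions are broader.** Section 11.0 (serious adverse events) covers any neurologic or musculoskeletal toxicity of grade 3 or higher. Section 14 (halt) uses grade 3 or higher or the Section 11.0 definition. Section 4.1 (evaluation of severe toxicities) uses grade 3 or higher with no term list. Section 2.0 reads as broad but cites Appendix 2. Only that appendix's title, in Section 20.0, was available here, so its terms could not be checked.

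**3. The plan's own figures.** Section 14 expects fewer than 2 events in 20 patients, citing a rate of about 3% (Section 3.4: 1/37 = 2.7%). Expected number: 20 × 0.03 = 0.6. P(0 or 1) = 0.97^20 + 20 × 0.03 × 0.97^19 = 0.880. The statement is consistent with its input, and no stated figure is disputed.

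Other rates in the documents give:
- neurological toxicity on the order of 5% (Section 3.4): 20 × 0.05 = 1 patient;
- severe neurologic or musculoskeletal toxicity under 10% (Section 11.0): fewer than 20 × 0.10 = 2 patients;
- rare acute complications, spine fracture among them, under 1% (Section 11.0): fewer than 20 × 0.01 = 0.2 patients.

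No rate is given for late fracture, or for nerve injury separately from other neurological toxicity.

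**4. Step size.** With 20 evaluable patients, each patient whose only severe event is left out lowers the rate by 1/20 = 5 percentage points. As an illustration only, with exact (Clopper-Pearson) 95% intervals:
- 2/20 = 10% (1.2% to 31.7%);
- 1/20 = 5% (0.1% to 24.9%).

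The intervals overlap almost entirely. The illustration shows how coarse a rate on 20 patients is. It does not estimate a bias.

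**The case against.** The best defence is that Section 12.0 describes an instrument and does not define the endpoint. The musculoskeletal sentence limits a panel of questions about symptoms, and a panel that does not ask about fracture is not a rule that fracture goes uncounted. Fracture could be seen on the follow-up imaging, and adverse event assessment is a separate row in the Section 10.0 schedule. Section 11.0 documents all adverse events at least possibly related to therapy. No section says that the safety rate will be tabulated from the four terms.

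Much of this stands, and it is why the consequence is put conditionally. It is weaker for the neurological sentence, which limits categories of evaluation and not questions. It also does not remove Section 11.0's reference to Section 12.0 for grading.

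Two stronger readings are tempting and not supported:
- **That the trial could fail to halt.** Section 14 uses grade 3 or higher or the Section 11.0 definition. The disability and hospitalization criteria for a serious adverse event need no grade.
- **That Section 12.0 certainly contradicts Section 2.0.** Section 2.0 cites Appendix 2. If the appendix holds only the same four terms, the two sections may agree and the problem is one of omission. If it is wider, Section 12.0 is the inconsistent text.

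**Conclusion.** The point holds as a minor inconsistency. The Section 12.0 restriction does not fit Section 11.0's naming of fracture, its definition of a serious adverse event, or the nerve injury named in Section 3.4. If the safety summary were built from the four terms, the severe-toxicity rate could be understated and would not be comparable with the under-10% expectation.

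The size is unknown: 5 percentage points per patient left out of 20, and zero if every related event of grade 3 or higher is counted. This assumes 20 evaluable patients and no other counted severe event in the patient concerned.

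A reader might infer that moving from 10% to 5% would change a study conclusion. It would not change a stated one. Section 2.0 sets no numerical acceptable level, the figure in Section 11.0 is an expectation and not a success criterion, and the objective is descriptive. The primary feasibility endpoint is untouched.

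**What to change.** Reconcile Section 12.0, and Appendix 2 if needed, with Sections 2.0, 3.4 and 11.0:

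1. In both Section 12.0 sentences, replace 'limited to' with 'including at least'.
2. Add the CTCAE v4.0 terms for spine or pelvic fracture and for radiculopathy or peripheral nerve injury, and align Appendix 2 if it lacks them.
3. State that every CTCAE v4.0 event of grade 3 or higher, at least possibly related to treatment, counts toward the safety objective.

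No separate rule is needed for events that may also be recorded as progression, because the relatedness test in Section 2.0 already governs attribution.

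The cost is an amendment of wording and perhaps a case report form change. Examination with neurological and ambulation assessment, imaging and adverse event assessment are already scheduled in Section 10.0, so no new procedure is required. The downside is that a few more events may be reported.

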13.0 CRITERIA FOR REMOVAL FROM STUDY

The study subject will be removed from the study for any of the following after review by the primary investigator:

1. If a change in the patient's medical status unrelated to HDR brachytherapy results in the patient being unable to comply with the protocol.
2. Patient is unable to comply with the follow up requirements of the protocol.
3. Patient request. Patients will be able to withdraw at any time without cause or reason.

4. If the attending radiation oncologist believes that the patient will be adversely affected by any aspect of the treatment.

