14. BIOSTATISTICS

This is a pilot interventional study to evaluate the feasibility of high dose rate (HDR) brachytherapy using image-guided navigational techniques as salvage therapy for previously treated lesions of the spine. The primary outcome that we wish to assess is the reproducibility of the treatment plan parameters; secondary outcomes include toxicity, relief of pain, and local disease progression.

In terms of technical feasibility, a patient is regarded as being successfully treated if the target D90 is $\geq 80\%$ AND the cord/cauda max dose is 8 Gy. To this end we will enroll 20 patients and declare the procedure feasible if at least 15 patients can be successfully treated. For this decision rule we have the following probability table:

True feasibility rate	55%	60%	65%	70%	75%	80%	85%	90%
Probability of declaring feasible	0.055	0.126	0.245	0.416	0.617	0.804	0.933	0.989

We believe this procedure will be quite safe for patients; a previous study from Japan [Seichi 1999] showed serious toxicity rates of approximately 3%, and we anticipate ours will be even lower. Among the 20 patients we expect to see less than 2 adverse events. In the event that a second serious adverse event (\geq Grade 3, or as otherwise defined above in Section 11.0) occurs, this protocol will be immediately halted and the investigator will carefully examine the cases with the assistance of the co-principal investigator and at least one investigator from both Medical Physics and Radiology and review the protocol (to be either terminated or modified in order to proceed further). Self-reported pain scores will be recorded and descriptive statistics regarding time to, degree of, and duration of relief from pain (if any) will be summarized numerically and/or graphically. In-field progression-free probability will be estimated using Kaplan-Meier estimation.

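### Section 13 takes patients who cannot keep up with follow-up off study without saying that outcome data continue, so late toxicity and progression could look better than they are

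*Combined protocol and SAP*

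**What the plan says.** Section 13 is written as a mandatory rule: "The study subject will be removed from the study for any of the following after review by the primary investigator". Four reasons follow.

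- Item 1: "If a change in the patient's medical status unrelated to HDR brachytherapy results in the patient being unable to comply with the protocol".
- Item 2: "Patient is unable to comply with the follow up requirements of the protocol".
- Item 3, patient request: "Patients will be able to withdraw at any time without cause or reason".
- Item 4: "If the attending radiation oncologist believes that the patient will be adversely affected by any aspect of the treatment".

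Items 3 and 4 carry no time limit. Section 13 does not say whether outcome data are still collected after removal.

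The outcomes at stake are set elsewhere. Section 12 evaluates toxicity to one year after treatment and counts spinal cord, cauda or nerve compromise as progression. Section 11 defines late toxicity as running from 90 days to 1 year and says that the serious neurologic and musculoskeletal events tend to appear late. Section 14 halts the protocol at a second SAE and estimates in-field progression-free probability by Kaplan-Meier, with no censoring rule for removed patients.

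The primary rule in Section 14 is: "To this end we will enroll 20 patients and declare the procedure feasible if at least 15 patients can be successfully treated". Section 12 places the dosimetric evaluation after implantation and before treatment. Neither section says how a removed patient counts or whether one may be replaced.

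**The concern.** A patient who loses ambulation or declines neurologically is among those least able to attend visits. Item 2 can therefore end observation because of the very outcome being measured. Item 1 has a similar weakness: it rests on an unblinded judgement that the change is unrelated to treatment, which is hard to make when myelitis, fracture and tumour progression can look alike in their early stages.

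Three results depend on what happens to these patients: the late-toxicity rate, the halt at the second SAE, and the Kaplan-Meier estimate, which assumes that censoring is unrelated to prognosis. Section 1 expects the study to take four years, so late events in early patients would arise while others are still to be enrolled. The halt therefore relies on seeing them.

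There is a smaller question on the primary endpoint. Because items 3 and 4 can act after dosimetry is known and before treatment, the handling of such a patient in the count of 20 should not be left open.

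**Working it through.** **The plan's own figures.** With X ~ Bin(20, p), P(X ≥ 15) at p = 0.55, 0.60, 0.65, 0.70, 0.75, 0.80, 0.85, 0.90 is 0.0553, 0.1256, 0.2454, 0.4164, 0.6172, 0.8042, 0.9327, 0.9887. This reproduces every entry in the Section 14 row "Probability of declaring feasible". The table therefore assumes that all 20 patients are counted.

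**When late outcomes can be seen.**
- Visits (Section 10) fall at about 2, 5, 8 and 11 months, each ± 2 weeks.
- The first visit window closes at about 61 + 14 = 75 days, before the late period opens at 90 days. All scheduled late information comes from the last three visits.
- Section 10 allows up to two of those three by telephone, without physical examination. At least 3 − 2 = 1 must be in person. A patient who cannot manage that one no longer meets the follow-up requirements, and item 2 applies.

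**Halt at the second SAE.** P(at least 2) = 1 − (1 − p)^n − n·p·(1 − p)^(n−1). The true rate p = 0.10 is an assumption, chosen because Section 4.1 treats grade 3 toxicity at that level as grounds to stop accrual. The numbers removed are also assumptions.
- n = 20: 1 − 0.1216 − 0.2702 = 0.608
- n = 16: 1 − 0.1853 − 0.3294 = 0.485
- n = 14: 1 − 0.2288 − 0.3559 = 0.415

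The lower two treat removed patients as contributing nothing, which overstates the loss for anyone observed for part of the year. They also assume that removal is unrelated to toxicity, which understates it if removal follows decline. Working instead from the share of events that goes unseen, with 20 patients: losing 25% gives an effective rate of 0.10 × 0.75 = 0.075 and a probability of 0.449; losing 50% gives 0.05 and 0.264.

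**Toxicity proportion.** Suppose 4 of 20 are removed and 1 event is seen in the other 16. The observed rate is 1/16 = 6.3%. Over all 20 the possible range is 1/20 = 5% (none of the four had an event) to 5/20 = 25% (all four did).

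**The 15-of-20 count under two unstated ways of handling removals.**

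| Handling | True rate | 0 | 1 | 2 | 3 |
|---|---|---|---|---|---|
| Failures removed and replaced, P(Bin(20 + k, p) ≥ 15) | 65% | 0.245 | 0.357 | 0.474 | 0.586 |
| Removed whatever the result, not replaced, counted as non-successes, P(Bin(20 − k, p) ≥ 15) | 80% | 0.804 | 0.673 | 0.501 | 0.310 |

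Columns are the number k of patients removed. The first handling raises the chance of declaring feasibility and the second lowers it.

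**The case against.** The strongest reply is that removal from study is not exclusion from analysis. Section 13 does not say that data are discarded or that denominators shrink, and Kaplan-Meier keeps a patient's time up to removal. Section 10 commits to evaluating every treated patient whether or not the dosimetric goals were met, allows telephone visits and accepts outside imaging, so one missed visit does not trigger item 2. An SAE seen on study would be reported under Section 17.2 and would count toward the halt. This is also a 20-patient pilot with descriptive secondary outcomes.

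Much of this stands, and it rules out saying that the results are biased; they could be. It does not close the gap. The Section 10 commitment sits in a sentence about complications, and Section 13 does not exempt treated patients from removal. Telephone contact is capped at two visits and omits the examination. Reporting covers events that are seen, whereas the concern is events after observation ends.

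A reader might also infer that the removal rules undermine the feasibility count, with failed implants dropped and replaced. The documents do not support that. Item 2 concerns follow-up, and the primary endpoint is fixed before treatment. No section provides for replacement. Section 9 sends a plan that cannot reach the target dose to treatment at the highest dose achievable within the constraints, not to removal. Only items 3 and 4, acting between implantation and treatment, or a later decision to exclude removed patients, could touch the count, and the effect could go either way.

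**Conclusion.** The point holds for the secondary outcomes. Followed as written, items 1 and 2 can end observation of patients whose decline is the outcome of interest, and the plan does not say that data collection continues. The likely direction is favourable to the treatment, on the assumption that inability to attend is more common among patients with toxicity or progression; the documents neither test nor exclude this. The size cannot be fixed without a removal rate. Under the assumptions above, the chance of seeing two SAEs at a true 10% rate falls from 0.608 to between 0.485 and 0.415 when 4 to 6 of 20 patients go unobserved.

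For the primary endpoint the point is only a clarification: the Section 14 table is correct for 20 counted patients, and one sentence would keep it so.

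**What to change.** In Section 13, state that:

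1. Items 1 and 2 end protocol visits only.
2. For any treated patient removed for any reason, severe toxicity, local progression and death continue to be collected from institutional records to the end of the planned follow-up, unless consent for data use is withdrawn.
3. All treated patients stay in the toxicity denominator and in the Kaplan-Meier analysis, censored at the last disease assessment if progression has not been seen. This belongs together with step 2: a full denominator without continued collection would count unobserved patients as event-free.

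Leave the clinical content of item 4 as it is.

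In Section 14, add that a patient with post-implant dosimetry keeps that result in the 15-of-20 count and is not replaced.

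The cost is a few sentences and a small amount of chart review at a single centre. No threshold, sample size or treatment rule changes.
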